The efficacy of **initial or repeated endodontic treatment** is affected by a number of preoperative clinical and technical factors. Clinically, pulp diagnosis, state of the canal (calcified canal, presence of a perforation) or the presence of a pre-operative peri-radical lesion can have a negative impact on the result. From a technical point of view, several root canal preparation and obturation techniques exist and studies have not led to the conclusion that one technique is superior to another (HAS 2008). Nevertheless, the level to which the root canal is filled at the apex is a deciding factor in the prognosis; full obturation of the root canal up to the X-ray apex is expected; in the case of under-filling (i.e. the canal is not completely filled and the X-ray image shows that the apical limit of the filler is less than 2 mm in relation to the X-ray apex), the result is a medium-term resumption of infection and necrosis of the remaining nervous and vascular tissues, leading to inflammation and pain and the need to undertake repeated endodontic treatment.

Based on two systematic reviews of the literature, Ng et al found that the efficacy rate (i.e. complete or partial cure) was 85.2% (IC95%: 82.2–88.3%) after initial root canal treatment and 77.2% (IC95%: 61.1–88.1%) after repeated endodontic treatment (Ng 2007; Ng 2008). These meta-analyses are based on dozens of clinical studies conducted over the last few decades, the methodologies for which vary widely, particularly in terms of the root canal filling cements used and the length of patient clinical follow-up after treatment (6 months to 20 years follow-up interval depending on the study; few studies had a follow-up of more than 4 years).

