6.1. General points and methodology

✓ Methodology — trial design

Prospective, multicenter, randomized, controlled, open-label study, with blind evaluation of the primary criterion and several secondary criteria (PROBE design).

Parallel group design (1:1):

- The arm receiving the device under investigation: PA1704
- The arm receiving the comparator medical device: BioRoot™ RCS.

✓ Measures to reduce or avoid bias.

Randomization and stratification:

Before the trial is set up, the CRO's biostatistician will computer-generate a block randomization list stratified by clinical indication (initial endodontic treatment (ET) versus re-treatment (ER)). The randomization system will be integrated directly into the electronic CRF.

Randomization will be carried out by the electronic CRF once the eligibility criteria have been checked, the clinical indication (ET or ER) has been determined and all this information has been recorded in the specific module by the investigator.

It should be noted that the proportion of ERs will be 30% of the overall sample, which is close to the rate reported in a French Health Insurance survey (Masson 2002). The rate of ER may vary between sites: some investigators, because of their specialty in endodontics, will include a majority of patients with an indication for re-treatment, whereas GP investigators will probably have more indications for first-line treatment.

Blind:

Investigators and patients will not be blind to the medical device allocated due to the different ways in which the 2 products are presented and used. On the other hand, two independent qualified assessors (previously calibrated under the supervision of the study coordinator) will conduct the blind, centralized review of the retro-alveolar X-rays taken at TO (reference radiograph obtained immediately post-operatively), 6 months, 12 months, 24 months, 3.5 years and 5 years (Refer to Section "Equipment to be used to evaluate clinical trial variables and arrangements for monitoring maintenance and calibration." section of this chapter); they will be blinded to centre, patient, indication (initial or repeat endodontic treatment), and treatment arm; the files will first be anonymized by the CRO.

✓ Outcome measures

Primary criterion (composite criterion):

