6.6.5. Data quality & monitoring

Data monitoring will be carried out by the CRO's CRAs, in accordance with Good Clinical Practice aimed at guaranteeing the quality of the trial. As the OPTIFILL trial is a category 1 RIPH involving a class IIa medical device that is not CE marked, the level of control will be high.

The CRAs will carry out regular remote monitoring *via* the ENNOV Clinical software application to track recruitment and check the integrity of the data entered into the eCRF. Requests for corrections or clarification of data will be sent to the investigator electronically.

In addition, the CRO's CRAs will regularly visit the investigating centres; 6 site visits are planned: 1 visit soon after the first enrolments, then a site visit after each follow-up visit provided for in the protocol, for up to 5 years of patient follow-up. The CRAs will check and verify consent forms, the consistency of critical data (PEC clinical criteria, AEs, patient record data, device defects) and equipment.

Visits will be organized after making an appointment with the investigator. The CRA must be able to consult:

- Consent forms,
- Observation and monitoring records,
- Patient source files (paper and/or electronic format),
- Medical devices made available (PA1704 and Bioroot™ RCS)
- Investigator file provided by the CRO.

7. Statistical considerations

7.1. Software used:

 Creation of the input template for the electronic CRF and patient record, database media: Ennov Clinical version 8.0,

Statistical analysis: JMP[®] version 15.0.0 or later (SAS Institute) on Windows 10 Pro.

7.2. Size of sample:

Based on the assumption that there is no difference in efficacy at 2 years between the 2 filling materials (PA1704 and BioRoot™ RCS) and that the expected efficacy rate of BioRoot™ RCS after initial and repeated endodontic treatment is 90% (Zavattini et al., 2019; Chybowski et al., 2018, Bardini et al., 2016), we calculate that a minimum of 66 subjects per group must be enrolled **to show non-inferiority of PA1704 over BioRoot™ RCS** with a confidence interval of 80%, a unilateral alpha risk of 5% and a 13% difference in efficacy tolerance between the 2 products (Ng 2007; Ng 2008; Eyuboglu 2016). By enrolling an additional 20% of patients in order to take into account those lost to or withdrawn from the trial, **the number of patients who must be included is 80 in each group, or 160 patients in total.**

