7.3. Degree of significance and power of the clinical trial

The main analysis will be carried out using a one-tailed statistical test with a significance threshold α set at 5%. The clinical trial is designed to ensure 80% power for the main analysis test. Secondary analyses will be carried out using two-tailed statistical tests with a significance threshold α set at 5%.

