7.7. Statistical methods

The statistical methods are based on the following elements and will be detailed in the Statistical Analysis Plan.

7.7.1. Sample description:

The description of the subjects enrolled who completed the trial and those enrolled who left prematurely will be presented using a table of absolute (N) and relative (%) frequency. Reasons for premature discharge and deviations from the protocol will be listed.

7.7.2. Descriptive analyses:

Clinical data collected at enrolment and at each visit will be described. Descriptive statistics will be presented according to the nature of the criterion analyzed:

- Quantitative variable: sample size, number of missing data sets, mean, standard deviation, median, minimum and maximum;
- Qualitative variable: absolute frequencies (N) and relative frequencies (%) per class in each group, number of missing data.

Graphs will be provided for each variable.

7.7.3. Comparative analyses:

A comparison of 2 independent means will be made using the Student's t-test; if the variances are unequal (verified by the Fisher's test), use the Welch's test instead of the Student's test. If the conditions for applying the Student test are not met (n < 30), the non-parametric Wilcoxon test is used.

2 independent percentages are compared using Pearson's Chi-2 test. If the conditions for application are not met (at least one theoretical number < 5), Fisher's exact test is used.

7.7.4. Analysis of primary performance criterion:

As a reminder, the primary performance criterion is the efficacy rate at 24 months of treatment based on clinical criteria assessed by the investigator (tooth functionality and pain level) AND radiological criteria assessed blind by independent reviewers (complete healing, reduction of lesions, failure). In the event of failure at 6 or 12 months, the patient will be considered to have failed at 24 months.

The primary criterion will be analyzed using 2 approaches, in accordance with the literature:

- **Primary analysis of soft criteria**: treatment rates with complete or incomplete cure are compared against failure rates;
- **Secondary analysis of strict criteria**: treatment rates with complete healing are compared against rates of failure or incomplete healing (complete healing can take up to 4 or 5 years).

The comparison of efficacy rates between the 2 groups will be carried out using the Dunnett and Gent χ^2 test (Dunnett CW and Gent M 1977; Elie C et al 2008).

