No interim analysis of the primary criterion is planned. The main analysis will only be carried out after the 2-year follow-up of all patients enrolled.

Two interim analyses of the secondary criteria have been planned. These will be carried out after 6 and 12 months' follow-up for all included patients.

The alpha risk will not be inflated, as the main criterion will not be analyzed in the interim analyses. Therefore, no alpha risk adjustment method is required. The final analysis will focus on the primary and secondary criteria.

For patients treated with the PA1704 ready-to-use filling material and who agree to be followed-up with for up to 5 years, a non-comparative descriptive analysis of secondary performance and safety criteria at 3.5 years and 5 years will be carried out at the end of their participation.

7.7.8. Criteria for stopping the clinical trial from a statistical point of view:

None. Interim analyses are only used to collect data on secondary criteria before the end of the study. The conclusion on the non-inferiority of PA1704 compared to BioRoot™ RCS will only be made on the final analysis at 2 years.

7.7.9. Changes to the statistical analysis plan:

The statistical analysis plan will be drawn up before the first interim analysis is carried out. The initial analysis strategy may undergo minor modifications following each data review, and the new statistical analysis plan will be described in detail at that time.

7.7.10. Specification of sub-groups for further analysis:

The following sub-group analyses will be carried out, at least on the PP population, during the final analysis at 2 years. Other factors not considered in this protocol may be added in the Statistical Analysis Plan.

- For the primary criterion, the rate of effective treatment at 2 years:
 - Prognostic factors at enrolment
 - Presence or absence of a periapical lesion,
 - Indication for endodontic treatment: initial versus repeat endodontic treatment,
 - Factors related to the surgical procedure
 - Type of rinse solution used to finalize root canal disinfection,
 - Operating techniques used: technical platform used (whether or not a microscope was used), manual files versus continuous rotation versus alternative rotation.
- Post-operative pain:
 - Operating techniques used: manual files versus continuous rotation versus alternative rotation.
 - Initial pulp pathology (pre-existing inflammatory situation or necrosis or live pulp),

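### The primary non-inferiority comparison adjusts for neither the randomisation stratum nor pre-operative lesion status: a valid analysis, but a modest and avoidable loss

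*Combined protocol and SAP*

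**What the plan says.** - **Primary analysis (7.7.4).** "The comparison of efficacy rates between the 2 groups will be carried out using the Dunnett and Gent" chi-square test. A one-sided 95% confidence interval for the difference in rates is added and compared with the margin. No stratum or covariate is named for either. The main analysis set is Per Protocol.
- **Randomisation (6.1).** The list is a "block randomization list stratified by clinical indication", meaning initial treatment (ET) or retreatment (ER). Lesion status is not a stratum.
- **Prognosis (3.1.2).** The protocol states that "the presence of a pre-operative peri-radical lesion can have a negative impact on the result". It gives no effect size. For indication it cites review rates of 85.2% (initial) and 77.2% (repeat).
- **Collection (6.5.2).** The presence of an apical lesion is part of the enrolment data at V1, and a pre-operative X-ray is taken at V0.
- **Planned use.** The synopsis adds an analysis of the primary criterion by covariates, including apical lesion at T0. Section 7.7.10 lists "Presence or absence of a periapical lesion" as a sub-group factor. Neither place defines an adjusted treatment difference or ties one to the margin.

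**The concern.** With roughly 66 evaluable patients per arm, lesion prevalence can differ between arms by chance. If lesion status affects success, the observed difference then moves in a known direction, and the primary estimate takes no account of it.

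The room is narrower than the 13-point margin suggests. At 90% success and 66 per arm, the one-sided 95% half-width is 1.645 × √(0.18/66) = 8.6 points. Non-inferiority is therefore missed once PA1704 is observed to be worse by more than about 13 − 8.6 = 4.4 points, or about three patients. A shift can produce a false claim as easily as a missed one.

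Timing matters too. Section 7.5 lets data reviews bring in factors not foreseen, 7.7.9 allows the analysis strategy to be modified after each review, and the arms are compared on efficacy at 6 and 12 months before the final analysis. An adjusted estimate named only after those looks would be open to challenge as data-driven.

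**Working it through.** **1. The plan's own figure.** Inputs from 7.2 and 7.3: the assumption that "the expected efficacy rate of BioRoot™ RCS after initial and repeated endodontic treatment is 90" per cent, with the same rate for PA1704; "a unilateral alpha risk of 5% and a 13% difference in efficacy tolerance between the 2 products"; and 80% power. With unpooled variance:

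n = 2 × 0.90 × 0.10 × (1.645 + 0.842)² / 0.13² = 65.9, so 66 per arm.

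This matches "a minimum of 66 subjects per group must be enrolled". Adding 20% gives 66 × 1.2 = 79.2, hence 80. Power at 66 is Φ(0.13/√(0.18/66) − 1.645) = 80.1%.

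**2. Gain from stratifying by lesion.** Let q be lesion prevalence and d the gap in success between teeth without and with a lesion, overall success held at 90%. The within-stratum variance is 0.09 − q(1−q)d², so the proportional reduction is q(1−q)d²/0.09. Neither q nor d is in the documents; the ranges are assumptions.

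| Gap d | Prevalence q | Success with / without lesion | Variance cut | Power at 66 |
|---|---|---|---|---|
| 5 points | 50% | 87.5 / 92.5 | 0.7% | 80.3% |
| 10 points | 30% | 83 / 93 | 2.3% | 80.9% |
| 10 points | 50% | 85 / 95 | 2.8% | 81.1% |
| 15 points | 30% | 79.5 / 94.5 | 5.25% | 81.9% |
| 15 points | 50% | 82.5 / 97.5 | 6.25% | 82.3% |
| 20 points | 30% | 76 / 96 | 9.3% | 83.4% |
| 20 points | 50% | 80 / 100 | 11.1% | 84.0% |

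Prevalence of 70% gives the same variance cut and power as 30% for gaps up to 10 points. Gaps of 15 points or more are impossible there, because success without a lesion would exceed 100%. The last row is the extreme: no failures at all in lesion-free teeth.

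**3. Chance imbalance.** The standard deviation of the between-arm difference in prevalence is √(2q(1−q)/66). At q = 50% this is 8.7 points, so P(|imbalance| > 10 points) = 2 × (1 − Φ(10/8.7)) ≈ 25%. At 30% or 70% the standard deviation is 8.0 points. A 10-point imbalance shifts the observed difference by 0.10 × d, which is 0.5 points at d = 5 and 2.0 points at d = 20. Against the 4.4 points of room, that is 0.5/4.4 = 11% to 2.0/4.4 = 45%.

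**4. The indication stratum.** As an illustration only, take the cited 85.2 − 77.2 = 8-point gap, the planned 30% of retreatments and 90% overall success. The same formula gives 0.3 × 0.7 × 0.08²/0.09 = 1.5% of variance.

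**5. Validity.** In simulation (200,000 runs, 66 per arm, true difference −13 points), the type I error of the unadjusted Wald comparison was 0.055–0.056. A Mantel-Haenszel difference stratified by lesion gave 0.057–0.059.

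**The case against.** The strongest reply is that nothing is broken. A reader might infer that an unadjusted test is biased or that its error rate is wrong. The documents do not support that: randomisation makes the comparison fair on average, and the simulated error rates bear this out. A reader might also count chance imbalance and lost precision as two harms. They are one. The variance due to imbalance, 2q(1−q)d²/66, divided by the total, 2 × 0.09/66, is q(1−q)d²/0.09, which is exactly the reduction in step 2. The unadjusted interval already carries it. What remains is that the trial will be read conditionally on the imbalance it actually has.

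Nor does the plan ignore lesion status. The synopsis and 7.7.10 both use it, and 7.7 leaves detail to the SAP. The gap is narrower: no adjusted difference is tied to the margin.

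The effect may also be small on this endpoint. Under the soft criterion in 6.1, uncertain efficacy counts as success, and only teeth with a lesion at T0 can be scored uncertain, while any new lesion in a lesion-free tooth is a failure. At a 5-point gap the simulated standard deviation of the estimate is 5.22 points with or without stratification. Sparse data are a fair worry too: with four strata in two arms, at least one of the eight cells has no failures in 91% or more of simulated runs.

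One counterpoint stands. The deciding set is Per Protocol and drops patients for post-randomisation reasons (7.6), so balance at allocation need not carry over. Stratification removes a lesion imbalance in that set, but does not cure selection.

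**Conclusion.** The point holds as an avoidable inefficiency. The primary comparison leaves out a baseline variable that the protocol itself treats as prognostic, and also the factor used to stratify randomisation. The planned secondary uses of lesion status do not fill the gap.

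The likely benefit is about 0–4 points of power and protection against shifts of about 0.5–2 points per 10-point imbalance. That rests on the assumed prevalence and gap; the upper end needs a gap near 20 points. What the text says is certain; the size of the effect is not.

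Two stronger readings should be resisted. One is that lesion status is a strong predictor here: 3.1.2 says only that it can worsen the result and gives no figure. The other is that the trial is undersized because the analysis is unadjusted: the 66 per group reproduces without adjustment, and "The clinical trial is designed to ensure 80% power for the main analysis test" is met at that number.

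**What to change.** Amend the synopsis, 5.2 and 7.7.4, and carry the same text into the SAP:

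- Make the primary estimate a risk difference stratified by indication (ET/ER) and pre-operative lesion (yes/no). Use a stratified score interval such as Miettinen-Nurminen, or Mantel-Haenszel, and compare its one-sided 95% lower limit with −13 points.
- Define lesion status as the investigator's pre-operative record, and require its entry in the eCRF before allocation. Section 6.1 currently requires only eligibility and indication.
- State a pooling rule for sparse strata in advance, based on stratum counts with the arms combined. About 0.10 × 132 = 13 failures are expected in total.
- Keep the unadjusted Dunnett-Gent result as a sensitivity analysis.

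The cost is a small protocol wording change as well as SAP text, and the pooling rule. No extra patients or measurements are needed. One limitation remains: Table 4 starts from the central readers' view of the T0 image, and the V0 image has no blind review, so the stratifying variable and the endpoint's baseline can disagree. Tabulate that disagreement by arm.

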If the patient is seen for treatment outside the protocol (routine care) or for any emergency, the investigator shall collect all the information relevant to the trial (date of consultation, reason for consultation, occurrence of AEs, etc.).

V3 — Clinical follow-up visit at 6 months (± 1 month) — Standard practice

- **Clinical examination**: Verification of the functional status of the treated tooth and percussion test (lateral and axial),
- Recording of AEs.
- Retro-alveolar X-ray check to evaluate the results of endodontic treatment at 6 months: 1) density of the root canal filling (radiopacity + presence of voids), 2) progress of resorption of the extruded material

where appropriate, **3)** apical lesion (absence/appearance/still present compared with T0) and progress of the size of an existing lesion (reduction, stabilization or increase).

Upload the 6-month follow-up retro-alveolar image to the eCRF (reminder: the entire tooth – from the *crown to the apex, including the root* – must be visible in the image; see chapter 6.1).

— The investigator shall evaluate the efficacy of the endodontic treatment on the basis of the clinical and radiological criteria identified (*Note: Only the evaluation of the radiological criteria by the independent reviewers will be taken into account for the primary evaluation criterion (PEC); the investigator's evaluation is to be used to determine further clinical follow-up*).

Procedure in the event of the appearance of a lesion or an increase in the size of a pre-existing lesion:

- If the investigator considers it to be an emergency (e.g. if the tooth is symptomatic and/or non-functional): the investigator will notify the patient of the failure of the endodontic treatment and schedule retreatment. In this case, the patient leaves the trial early due to the failure of the treatment and continues endodontic treatment outside the trial (end-of-trial form to be completed in the eCRF). Performance and safety evaluations now end. Failure notified at 6 months is carried forward as the PEC value (response at 24 months = failure). The patient will not be replaced.
- If the investigator considers that it is NOT an emergency (e.g. if the tooth is asymptomatic): medical advice should be sought from the trial coordinator (who will review the X-rays) before considering retreatment and early discharge from the trial for treatment failure.

V4 — Clinical follow-up visit at 12 months (± 1 month) — Standard practice

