In addition, the difference in the 2-year efficacy rate between the 2 materials are to be calculated; its unilateral confidence interval of 95% will be provided and the lower limit is will be compared against the non-inferiority limit.

The main performance analysis will be carried out on the PP population, in accordance with the recommendations for non-inferiority studies. This will be complemented by an analysis of the mITT population to check the stability of the results.

7.7.5. Analysis of secondary performance criteria:

Efficacy rate at 6 months based on radiological and clinical criteria: Description and comparison, between the PA1704 arm and the BioRoot™ RCS arm, of the 6-month efficacy rate by Pearson's Chi-2 test or Fisher's exact test.

Efficacy rate at 12 months based on radiological and clinical criteria: Description and comparison, between the PA1704 arm and the BioRoot™ RCS arm, of the 12-month efficacy rate by Pearson's Chi-2 test or Fisher's exact test.

Quality of apical obturation at T0 (complete obturation, under-filling or over-filling): Description and comparison, between the PA1704 arm and the BioRoot™ RCS arm, of the proportions of apical obturation quality by Pearson's Chi-2 test or Fisher's exact test.

Density of root canal filling at T0, 6 months, 12 months, 24 months: Description and comparison at each time point, between the PA1704 arm and the BioRoot™ RCS arm, of the proportions of canals with an

obturation density deemed sufficient and the proportions of canals free of voids, by Pearson's Chi-2 tests or Fisher's exact tests.

Progress of material resorption over 24 months, in the event of over-filling at T0 (6 months, 12 months and 24 months): Description and comparison, between the PA1704 arm and the BioRoot™ RCS arm, of the proportions of patients with resorbed materials among patients who were over-filled at T0 by Pearson's Chi-2 test or Fisher's exact test.

Pre-operative and post-operative pain experienced by the patient (VAS 0-100 mm) at T0 (end of surgery), 12h, 24h, 48h, 72h and 7 days: For each time point, description and comparison of the pain, between the PA1704 arm and the BioRoot™ RCS arm, by a Student, Welch or Wilcoxon test. A figure representing average pain as a function of assessment times per arm will be provided. The causes of the pain will be described.

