 - o Preoperative pain (symptomatic tooth at enrolment, preoperative VAS).

7.7.11. Handling missing, unused or erroneous data, including drop-outs and withdrawals:

No imputation method is planned. However, as stated above, patients with treatment failure at 6 or 12 months will be withdrawn from the study and will be considered to have treatment failure at 24 months.

7.7.12. Exclusion of certain information from the hypothesis tests, if relevant:

None.

7.7.13. In the case of multi-center investigations, minimum and maximum number of subjects to be included for each center:

Each center will include 22 to 24 patients with an indication for initial or repeat endodontic treatment. The number of repeat treatments may vary between centers, but will total 30% in the sample. Some investigators, because of their specialty in endodontics, will include a majority of patients with an indication for repeat treatment, whereas GP investigators will probably have more indications for first-line treatment.

8. Data management

Procedures for examining data, cleaning databases, issuing and resolving data queries:

See Chapter 6.6, Data quality and monitoring section.

Procedures for verification, validation and securing of the electronic clinical data systems, where applicable:

The data collected in electronic CRFs is recorded directly in an electronic database using ENNOV software and hosted on a secure health data server in accordance with current regulations. The data collected in the paper logbooks is entered by the CRO into the electronic database using ENNOV software.

Data retention:

See the Archiving section in Chapter 12.4.

9. Amendments to the clinical investigation plan

Requests for substantial modifications will be sent by the CRO, on behalf of the sponsor, to the relevant ethics committees for their opinion and to the competent authorities for authorization, in accordance with law 2004-806 of 9 August 2004 and its implementing decrees in force.

Similarly, non-substantial modifications will be sent for information.

An updated version of the amended protocol must be dated. This new version will be sent to the investigators.

The patient information leaflet should be amended if necessary.

10. Deviations from the clinical investigation plan

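### A patient who leaves for treatment failure at 6 months has no value in the 12-month efficacy comparison, which overstates 12-month efficacy and can bias the difference in either direction

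*Combined protocol and SAP*

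**What the plan says.** The carry-forward rule appears in three places, and for a 6-month failure each names 24 months as the only target.

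- Section 6.5.2, visit V3: "Failure notified at 6 months is carried forward as the PEC value (response at 24 months = failure").
- Section 7.7.4: "In the event of failure at 6 or 12 months, the patient will be considered to have failed at 24 months".
- Section 7.7.11: "No imputation method is planned", with one exception, that patients failing at 6 or 12 months "will be withdrawn from the study and will be considered to have treatment failure at 24 months".

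For a patient who leaves for urgent retreatment after V3, section 6.5.2 adds: "Performance and safety evaluations now end". Efficacy at each check-up combines that visit's X-ray reading with that visit's clinical findings (section 6.1, Table 4), and the second central review campaign reads the 12-month image.

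Section 7.7.5 plans a description and between-arm comparison "of the 12-month efficacy rate by Pearson's Chi-2 test or Fisher's exact test". It gives no rule for patients who failed earlier. Section 7.7.7 schedules this at the interim analysis after 12 months of follow-up.

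**The concern.** The 12-month rate needs an examination and an image that a patient who left at 6 months cannot have. The failure is known, is counted in the 6-month rate and is counted again at 24 months, but the plan gives it no value in between.

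If these patients drop out of both numerator and denominator, the 12-month comparison is made in a group selected on outcome after randomisation. The decision to leave rests with an investigator who knows which sealer was used. Each arm's 12-month rate then describes only those who had not already left as failures. The published sequence of 6-, 12- and 24-month rates can also show efficacy falling after 12 months when no new failure has occurred. Section 3.1.2 treats 12 months as the minimum period for judging efficacy, so readers will look at this rate.

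**Working it through.** **The plan's own figure.** The sample size concerns only the 24-month test. With 90% in both arms, a 13-point margin, one-sided 5% and 80% power: n = (1.645 + 0.842)² × 2 × 0.9 × 0.1 / 0.13² ≈ 65.9, so 66 per group, as stated in section 7.2. Then 66 × 1.2 = 79.2, taken as 80. Nothing below changes this.

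**Inputs for the 12-month check.** The documents give no 6- or 12-month failure rate and no exit rate. I borrow 90% (the 24-month planning rate, section 7.2) and 77% (90 minus the 13-point margin) as 12-month rates. I assume that a share e of failures leaves at 6 months, with e = 25, 50 or 75%.

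**Formula.** With true efficacy p, omitting the leavers removes (1 − p)e from the denominator and nothing from the numerator:

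reported rate = p / (1 − (1 − p)e)

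**Same exit share in both arms**

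| e | p = 0.90 | p = 0.77 | Reported difference (true −13) |
|---|---|---|---|
| 25% | 0.90/0.975 = 92.3% | 0.77/0.9425 = 81.7% | −10.6 |
| 50% | 0.90/0.95 = 94.7% | 0.77/0.885 = 87.0% | −7.7 |
| 75% | 0.90/0.925 = 97.3% | 0.77/0.8275 = 93.05% | −4.2 |

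At e = 50%, an arm truly at 90% at both 12 and 24 months would be reported as 94.7% and then 90.0%: an apparent fall of 4.7 points with no new failure.

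**Different exit shares (PA1704 77%, BioRoot RCS 90%)**

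- 25% v 50%: 81.7% v 94.7%, difference −13.0, unchanged. The leavers are 0.23 × 0.25 = 5.75% of the PA1704 arm and 0.10 × 0.50 = 5.0% of the BioRoot RCS arm.
- 25% v 75%: 81.7% v 97.3%, difference −15.6, enlarged. The leavers are 5.75% v 7.5%.

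**The same in assumed counts, 80 per arm, PA1704 v BioRoot RCS**

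| Failures leaving at 6 months | Later failures by 12 months | Leavers counted as failures | Leavers omitted |
|---|---|---|---|
| 8 v 2 | 4 v 4 | 68/80 v 74/80: −7.5 | 68/72 v 74/78: −0.4 |
| 4 v 4 | 8 v 3 | 68/80 v 73/80: −6.25 | 68/76 v 73/76: −6.6 |
| 6 v 2 | 2 v 6 | 72/80 v 72/80: 0.0 | 72/74 v 72/78: +5.0 |
| 2 v 6 | 8 v 2 | 70/80 v 72/80: −2.5 | 70/78 v 72/74: −7.6 |

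Every arm with early leavers has its rate raised. The difference shrinks when the worse arm loses clearly more of its patients at 6 months. Otherwise it can stay about the same, grow, or appear where there is none.

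**The case against.** **The omission is inferred, not stated.** No sentence defines the 12-month denominator as the patients examined at 12 months. These patients stay in the mITT population, which needs performance data at only one of the three time points. Their carried-forward primary value means that they are not removed from the PP population for lacking it (section 7.6). Section 7.7 leaves detail to a Statistical Analysis Plan, which section 7.7.9 says is drawn up before the first interim analysis. This stands in part: the documents do not order these patients excluded. But they do take a position, no imputation with one exception aimed at 24 months, and a plan written to match would leave the 12-month value missing.

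**The direction is not fixed.** A reader might infer that the omission always understates a difference between the sealers because the worse arm loses more patients. The documents say nothing about when failures occur in each arm, and the unequal-share cases above contradict that inference. This objection stands in full.

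**The exit route is narrow.** V3 acts only on a new or enlarged lesion. Immediate exit applies when the investigator judges an emergency; otherwise "medical advice should be sought from the trial coordinator (who will review the X-rays) before considering retreatment and early discharge from the trial", and a patient who stays is seen at 12 months. Table 4 also rates a stable lesion in a symptomatic or non-functional tooth as ineffective, yet the V3 procedure does not address that case. So not every 6-month failure leaves, and the 75% share is probably extreme. This stands, and it exposes a second gap, because 7.7.11 reads as if every such failure is withdrawn.

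**The consequence is limited.** The 12-month rate is secondary and the trial is not powered for it. There is no statistical stopping criterion, and the failures remain visible in the 6-month rate and in the listed reasons for discharge. This also stands.

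**Conclusion.** The point holds as a gap with a predictable effect on rates and an unpredictable effect on the comparison. Followed as written, the plan gives no 12-month value to a patient who leaves for failure at 6 months, so the 12-month efficacy rate is too high in any arm that has such patients.

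Under equal exit shares of 25 to 75%, the overstatement at a true 90% is 2.3 to 7.3 points, and a true −13 points is reported as −10.6 to −4.2. These sizes are illustrative. They rest on assumed exit shares and on planning rates borrowed from 24 months, and only patients who actually leave count towards them.

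A reader might go further and infer that the non-inferiority conclusion is compromised. The documents do not support that: the same failures are counted at 24 months, and section 7.7.8 rests the conclusion on the 2-year analysis alone. The point is worth correcting before the 12-month interim analysis, but it does not threaten the primary result.

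**What to change.** In sections 7.7.11 and 7.7.5, and in the V3 text of 6.5.2, state that a patient withdrawn for treatment failure at 6 months is counted as ineffective in the 12-month rate as well as at 24 months, and stays in the denominator. The rate among patients still followed at 12 months may be shown as a descriptive extra, labelled as such.

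Separately, reconcile 6.5.2 with 7.7.11 on which 6-month failures leave the trial, so that the patients covered by the rule are defined. Which of the two applies is for the sponsor and investigators to settle.

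The change extends the sponsor's own 24-month rule, needs no new data and leaves the sample size alone. Its cost is slightly less favourable 12-month rates.
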